#### 8.7.6 Death Events

AEs leading to death will be recorded and analyzed (for details see Section 10.3.3). Deaths will also be followed up during survival follow-up. After treatment discontinuation, information on survival follow-up and new anti-cancer therapy (including but not limited to targeted therapy and immunotherapy) will be collected via phone calls, patient medical records, and/or clinic visits approximately every 3 months until death (unless the patient withdraws consent for survival follow-up or the sponsor terminates the trial). If a patient requests to be withdrawn from survival follow-up, this request must be documented in the source documents and signed by the investigator.

Deaths clearly related to the progression of the disease will not be documented and reported as AEs or SAEs. These deaths must be collected on the death page of the eCRF.

In Germany only: Any death, irrespective whether causally related to disease progression or not, will be documented as AE and reported as SAE.

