#### **Period of observation:**

- The period of observation starts after informed consent has been obtained. After informed consent, all AEs and SAEs should be reported until 60 days after the last dose of trial treatment.
- AEs occurring later than 60 days after the last trial treatment must only be documented if a relationship to trial treatment or trial procedure is suspected.

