The number and percentage of patients with TEAEs will be summarized by 'ALL' and 'Related' to trial treatment (BNT411, atezolizumab, carboplatin, and etoposide) by PT nested within SOC. If an AE is reported more than once by the same patient for a SOC / PT the related AE will be counted once for this SOC / PT. The relationship to trial treatment will be counted as related if relationship status is reported as missing for an AE.

TEAE by NCI-CTC grade

The number and percentage of patients with TEAEs will be summarized by worst NCI-CTC grade by PT nested within SOC. Worst grade will be counted if an AE is reported more than once by the same patient for a SOC / PT. The related TEAEs by worst NCI-CTC grade will be summarized separately.

The number and percentage of patients with grade ≥ 3 AEs and related grade ≥ 3 AEs will be summarized by PT nested within SOC. In addition, AEs with a missing grade will be presented in the summary table as a grade category of “Missing.”

Deaths

- All deaths including those that occurred on-treatment (on or after date of first dose of BNT411) and post-treatment, will be listed, post-treatment deaths will be flagged. In addition to the summary of on-treatment deaths an additional summary of all deaths (on-treatment + post-treatment) will be provided along with primary reason for death.
- A separate summary of TESAEs leading to death will be provided by PT nested within SOC.
- A separate summary of related TESAEs leading to death will be provided by PT nested within SOC.

Serious Adverse Events and Other Significant Adverse Events

The number and percentage of patients

- with any TESAE,
- with any related TESAE (separately for each trial treatment and total),
- with any TESAE leading to death,
- with any related TESAE leading to death,
- with any TEAE leading to permanent discontinuation of treatment (BNT411, atezolizumab, carboplatin, and etoposide), or
- with any TEAE leading to dose reduction or interruption

will be summarized by PT nested within SOC by cohort within each trial part.

Deaths

In addition to a summary of on-treatment (on or after date of first dose of BNT411 until...) deaths and primary reason for death an additional summary of all deaths (on-treatment + during follow-up) will be provided along with primary reason for death. by cohort for each trial part. All deaths including those that occurred on-treatment and during follow-up, will be listed, post-treatment deaths will be flagged.

AE listings

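### SAP 8.5.2 gives the on-treatment death window no end date: read literally, one Deaths block makes every Safety-set death on-treatment, and the other breaks off unfinished

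*SAP*

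**What the plan says.** SAP 8.5.2 has two blocks headed Deaths, one on each side of the block on serious and other significant adverse events.

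- **First block.** Its listing sentence begins "All deaths including those that occurred on-treatment (on or after date of first dose of BNT411) and post-treatment, will be listed", and goes on to require a flag for the post-treatment ones. Beside the on-treatment summary it plans a second one, in which "all deaths (on-treatment + post-treatment) will be provided along with primary reason for death".
- **Second block.** It covers the same outputs, but the window is now "on-treatment (on or after date of first dose of BNT411 until...) deaths and primary reason for death". Nothing replaces the dots. The other category also gets a second name: "All deaths including those that occurred on-treatment and during follow-up, will be listed, post-treatment deaths will be flagged".

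Other places bear on the window without defining it for deaths:

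- SAP 7.1 defines the Safety set by receipt of at least one BNT411 dose.
- SAP 8.5.2 limits treatment-emergent events to onset within 60 days of the last trial treatment; later events count only if related.
- Protocol 10.3.3, under the period of observation, says "After informed consent, all AEs and SAEs should be reported until 60 days after the last dose of trial treatment".
- SAP 8.2 describes patients as off treatment once they have discontinued, for the disposition tables.
- Deaths are collected well after dosing. SAP 3.2 has 12-weekly survival contact up to 1 year after the last dose; Protocol 8.7.6 has contact "approximately every 3 months until death".

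**The concern.** A split into on-treatment and post-treatment deaths needs a date at which the first period ends. The SAP asks for the split in a summary and in a listing flag but gives no such date. A programmer who follows the first block will produce an on-treatment table identical to the all-deaths table and a flag that never fires. One who follows the second block has to invent the cut-off.

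The affected table matters because it is the planned count of deaths from any cause close to exposure in a first-in-human trial. The tables of treatment-emergent serious events leading to death do not replace it. Under Protocol 8.7.6, 8.7.7 and 10.3.3, deaths clearly due to progression are not recorded as adverse events, except in Germany, where all deaths are. The fatal-event tables therefore rest on two country rules. An all-cause on-treatment table would not have that problem, provided its window were defined.

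**Working it through.** The SAP states no figure here, so there is none to reproduce. The check is to apply each rule to the Safety set and then look for a closing date elsewhere.

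**Step 1: first block.** Let B be the date of first BNT411 dose and D the date of death. The rule is: on-treatment if D ≥ B. By SAP 7.1 every Safety-set patient has a B, and no patient can be dosed after death, so D ≥ B always. Result: 100% of deaths are on-treatment, 0 are flagged, and the on-treatment summary equals the all-deaths summary. This contradicts the block's own post-treatment category and flag.

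**Step 2: second block.** The rule is: on-treatment if B ≤ D ≤ E, with E not given. The split cannot be computed.

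**Step 3: search for E.** The 60-day limit in SAP 8.5.2 applies to onset of adverse events. The 60 days in Protocol 10.3.3 apply to reporting of adverse events. The off-treatment description in SAP 8.2 applies to disposition. None is linked to the death tables.

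**Step 4: how much the choice of E matters.** Take four assumed deaths at 10, 45, 90 and 200 days after the last dose. These times are illustrative and not from the documents. A death at day d is on-treatment if d ≤ w.

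| Limit w after last dose | On-treatment | Post-treatment | All deaths |
|---|---|---|---|
| none (first block as written) | 4 | 0 | 4 |
| 60 days | 2 (days 10, 45) | 2 | 4 |
| 30 days | 1 (day 10) | 3 | 4 |
| 0 days | 0 | 4 | 4 |

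The total is 4 in every row; only the split moves.

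**Step 5: last dose of which drug.** Protocol 7.2.2 and Table 1-2 allow for atezolizumab, carboplatin or etoposide to stop 21 days or more after BNT411. Suppose the last of them stops exactly 21 days later and the patient dies 70 days after the last BNT411 dose (both assumed). Counted from BNT411, 70 > 60, so the death is post-treatment. Counted from the last drug, 70 − 21 = 49 ≤ 60, so it is on-treatment. In Part 1B the reference drug must therefore be named as well.

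**The case against.** The strongest reply is that this is an unfinished sentence, not a chosen rule. Both blocks name a later category, both require a flag, both plan a separate all-deaths summary, and the second block's dots show that an end was intended. That stands: a reader might infer that the report will class every death as on-treatment, but the SAP as a whole does not say so. It does not remove the defect, because the only complete rule on the page gives that result if followed. Nothing marks the dots as a redaction, and the first block has no gap at all.

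The second reply is that the lethality evidence does not rest on this table. This also stands. Fatal treatment-emergent events, part of the primary endpoint, have their own 60-day rule. Total deaths appear in the disposition summary (SAP 8.2), all deaths are summarized with primary reason, and every death is listed. The trial tests no hypothesis, and the MTD is assessed from DLTs in the DLT evaluation set.

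The third reply concerns the remedy: a 60-day death window is not identical to the treatment-emergent window. In Part 1B the latter starts with the first of any trial drug, normally a day before BNT411. That difference cannot reclassify a Safety-set death, since none can precede the first BNT411 dose. The difference at the far end is real. A related event starting on day 70 counts as treatment-emergent, while a death from it would be post-treatment. The two sets of tables need a flag to reconcile them.

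**Conclusion.** The point holds as an incomplete and internally conflicting definition. The on-treatment/post-treatment split of all-cause deaths is wrong if the first Deaths block is followed and undefined if the second is. The damage is confined to the on-treatment death summary and the post-treatment flag.

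Two stronger readings are tempting and should not be drawn.

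- **A multiple by which on-treatment deaths are overstated.** This would need survival, time on treatment and length of follow-up. The documents give neither of the first two, and they disagree on the third (1 year after last dose in SAP 3.2, until death in Protocol 8.7.6). It would also take a 60-day window as the truth.
- **Earlier, lower-dose cohorts showing more on-treatment deaths merely because they are followed longer.** Sequential escalation makes this conceivable under the first block, but nothing in the documents shows that it happens.

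The conclusion itself rests only on the two Deaths blocks, the Safety set definition, and the absence of a closing date elsewhere. The counts in the working illustrate sensitivity and are not estimates for this trial.

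**What to change.** In SAP 8.5.2, delete one of the two Deaths blocks and in the other:

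1. Define an on-treatment death as one from the first dose of BNT411 to 60 days after the last dose of any trial treatment: BNT411 in Part 1A, the latest of the four drugs in Part 1B. This follows the 60-day limit already used for treatment-emergent events and for the protocol's period of observation.
2. Call every later death post-treatment, and drop the alternative term for follow-up deaths.
3. Flag any post-treatment death that results from a treatment-related serious treatment-emergent event, so that the death and fatal-event tables reconcile. The same flag should cover a fatal event that starts inside the window when the death falls outside it.

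The cost is a few lines of SAP text; the dates are already collected and no other analysis changes. There is a small downside: 60 days is a convention, and the sponsor must confirm it. Two details should be settled at the same time. Protocol 10.3.3 counts the 60 days from the last trial treatment in one place and from the last IMP in another, and by Protocol 6.1 only BNT411 is an IMP in the USA and UK, against all four drugs in Spain and Germany. Protocol 7.2.2 moves patients to survival follow-up when a new anti-cancer therapy starts, so the SAP should say whether that affects the classification; the rule above assumes it does not.

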8.5.3 Laboratory assessments

All laboratory assessments except for PK and biomarkers will be processed by local laboratories. Summaries of all laboratory data will be based on Safety set for each trial part (Parts 1A and 1B) and total within each trial part.

For the purposes of summarizing and presentation in tables and listings, all laboratory values will be summarized by cohort and presented in System International (SI) units. If a laboratory value is reported using a nonnumeric qualifier e.g., less than (<) a certain value, or greater than (>) a certain value, the given numeric value will be used in the summary statistics, ignoring the nonnumeric qualifier. The data as collected will be presented in the listings.

Clinical laboratory data to be summarized includes hematology, biochemistry, urinalysis, coagulation factors and endocrine tests. The safety laboratory parameters to be assessed are listed in Section 10.2 of the CTP. The scheduled time points for assessment are outlined in the SoAs (Section 10.4.1)

Continuous clinical laboratory variables at each protocol scheduled visit and its change from baseline to each post-baseline visit will be summarized using descriptive summary statistics for each parameter listed in CTP Table 10-1 by cohort. Categorical variables will be summarized using n and %.

Laboratory values that are below or above the reference ranges will be flagged.

Abnormal and clinically significant, abnormal and not clinically significant, and normal laboratory values will be summarized for each parameter by visit and cohort.

All laboratory data will be presented in the data listings. Abnormal clinical laboratory values will be flagged in the listing.

Serology and pregnancy results will be listed only.

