As BNT411 was developed to release cytokines such as IFN $\alpha$  at an EC50 range lower than the EC50 required for release of cytokines such as TNF $\alpha$ , IL-6, and IL-10, the sponsor gauges the risk of higher grade clinically relevant and unmanageable manifestations of elevated cytokines as low and this protocol addresses the probability of such risks with a risk management plan. Upon stimulation, it has been described for TLR7 agonists that lymphocytes egress to the periphery and return within 24 to 48 hours. This sequestration effect has been attributed to the secretion of IFN $\alpha$  (Perkins et al, 2012) and may present as transient lymphopenia due to redistribution rather than cytotoxicity. Frequent laboratory monitoring is planned to observe this expected effect.

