#### Immune-related AEs that are considered DLTs:

- Any Grade 4 irAEs regardless of duration.
- Grade 3 colitis that does not downgrade to Grade ≤2 within 3 days after onset of the event despite maximal supportive care including systemic corticosteroids or downgrade to Grade <1 or baseline within 14 days.
- Any Grade 3 or Grade 4 non-infectious pneumonitis regardless of duration.

- Any Grade 3 irAE, excluding colitis and pneumonitis, that does not downgrade to Grade ≤2 within 3 days after onset of the event despite maximal supportive care including systemic corticosteroids or downgrade to Grade ≤1 or baseline within 14 days.
- Any Grade 2 pneumonitis that does not resolve to Grade ≤1 within 3 days of the initiation of maximal supportive care.
- Liver transaminase elevation higher than 8×ULN or total bilirubin higher than 3×ULN.
- Any other toxicity that is greater than baseline grade, is clinically significant and/or unacceptable, and is judged to be a DLT by the investigator and the sponsor.
- The definition excludes the following conditions:
  - o Grade ≤4 lymphopenia which is not considered clinically significant by the investigator.
  - o Grade 3 endocrinopathy that is managed with or without systemic corticosteroid therapy and/or hormone replacement therapy and the patient is asymptomatic.
  - o Grade 3 inflammatory reaction attributed to a local anti-tumor response (e.g. inflammatory reaction at sites of metastatic disease, lymph nodes) that resolves to Grade ≤1 within 3 weeks.
  - o Concurrent vitiligo or alopecia of any AE grade.

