## **Events NOT Meeting the AE Definition**

- Any clinically significant abnormal laboratory findings or other abnormal safety assessments which are associated with the underlying disease, unless judged by the investigator to be more severe than anticipated for the patient's condition. The disease/disorder being studied or expected progression, signs, or symptoms of the disease/disorder being studied, unless more severe than expected for the patient's condition. However, specific symptoms at time of progression that are considered to be caused by other reason, and fatal cases where other reason rather than the PD may not be discarded and will have to be documented as AEs and reported as SAEs if applicable. In Germany only: Deaths related to disease progression will be documented as AEs and reported as SAEs.
- Any abnormal laboratory findings which are evaluated and documented in the source data as not clinically significant (e.g., an abnormal laboratory value without any clinical manifestation, such as transient lymphopenia after infusion of BNT411 due to redistribution), should not be documented as an AE.
- The disease/disorder being studied, or anticipated progression, signs, or symptoms of the disease/disorder being studied, unless more severe than anticipated for the patient's condition
- Medical or surgical procedure (e.g., endoscopy, appendectomy): the condition that leads to the procedure is the AE.
- Situations in which an untoward medical occurrence did not occur (social and/or convenience admission to a hospital).
- Anticipated day-to-day fluctuations of pre-existing disease(s) or condition(s) present or detected at the start of the trial that do not worsen.

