## **Documentation of particular situations**

Abnormal Laboratory Results and Vital Signs Values

Not every laboratory or vital signs abnormality needs to be documented as an AE. For laboratory/vital signs abnormalities, the following definitions and documentation rules apply:

A laboratory/vital signs abnormality is clinically significant if it:

- is a sign of a disease or syndrome. In this case, only the diagnosis of the causing disease or syndrome needs to be documented as an AE.
- results in specific symptom(s) but no diagnosis of a disease or syndrome can be made. In this case, only the symptom(s) need to be documented as AE(s).
- is not a sign of a disease or syndrome and does not result in specific symptoms but leads to a change in trial treatment or in a medical intervention. In this case, the laboratory/vital signs abnormality must be documented as an AE.

Any laboratory/vital signs abnormality for which none of the above-mentioned criteria are applicable are not clinically significant and should therefore not be documented as an AE.

Increased Body Temperature and Fever

The normal range for the body temperature is defined as >35°C to <38°C. For results within this range no source data entry for clinical significance is required, and no AE needs to be documented. If an investigator rates a body temperature result within this range as clinically significant, the clinical significance needs to be documented in the source data and an AE (e.g. with the term "body temperature increased") needs to be documented. For results out of this range, a source data entry for clinical significance is required and an AE needs to be documented. The AE should be described (verbatim) and rated (intensity) according to NCI CTCAE criteria v5.0:

- Fever Grade 1: 38°C 39°C
- Fever Grade 2:  $>39^{\circ}\text{C}$   $40^{\circ}\text{C}$
- Fever Grade 3:  $>40^{\circ}$ C for  $\leq 24h$
- Fever Grade 4: >40°C for >24h
- Fever Grade 5: death due to fever

Since fever is an anticipated reaction to BNT411 and the sponsor is very interested in details of body temperature changes, an increase of body temperature  $\geq 38$  °C should be rated as clinically significant and documented as an AE. Conversely, there should be very good reasons if an increase of body temperature  $\geq 38$  °C is rated as not clinically significant and is not documented as an AE.

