8 STATISTICAL ANALYSES

8.1 General considerations

Unless otherwise specified, the details mentioned are for trial Parts 1A and 1B. The summaries will be presented as cohort and total within trial part (Part 1A and Part 1B). The presentation of data for Part 2 will be included in a SAP amendment.

No formal statistical comparisons between cohorts/trial parts will be performed.

Continuous variables will be summarized by cohort and total (as specified) using the following descriptive statistics: number of patients with non-missing data (n), mean, standard deviation (SD), median, minimum (min) and maximum (max).

Categorical variables will be summarized by cohort and total (as specified) presenting absolute and relative frequencies (n and %) of patients in each category and the number of patients with missing data (missing category will be presented if there is one or more missing value). Percentages will be calculated based on the number of patients with non-missing data (n) in the particular analysis set as the denominator. The text (N=xx) in the tables denotes the number of patients in the analysis set within each cohort. For event-driven occurrence data (e.g., adverse event, concomitant medication, etc.) the percentages will be based on the number of patients in the analysis set (N). For reported visit data (e.g., gender, [Eastern Cooperative Oncology Group] ECOG performance status, etc.) the percentages will be based on the number of patients with non-missing values (n).

All data collected during the trial will be listed, the trial day will be presented as appropriate. The data will be sorted by trial part (Part 1A, Part 1B) cohort, patient number cycle (if applicable) and date of assessment (if applicable).

All analyses will be conducted using SAS® version 9.4 or higher.

Baseline is defined as last available value prior to first dose of any trial treatment (i.e., for Part 1A BNT411 and for Part 1B BNT411 or atezolizumab or carboplatin or etoposide).

Generally, if there are multiple assessments available for a particular day, the assessment that is closest to the day (and time if collected) of the first dose of any trial treatment (i.e., BNT411 or atezolizumab or carboplatin or etoposide) will be used as the baseline value in the summary/analyses.

Multiple values at post-baseline visits: if there are multiple post-baseline assessments available within a visit/day, the earliest value and corresponding date/time will be considered.

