Change from baseline: Unless and otherwise specified, will be calculated as follows:

Change from baseline = post-baseline assessment value – baseline assessment value.

If either the baseline or post-baseline assessment value is missing, the change from baseline is set to missing as well.

For the derivations of PK and PD data, see Section [8.6.1](#) and [8.6.2](#).

Duration (Other than “Trial Treatment Duration” defined in Section [8.5.1](#)) will be calculated as follows:

- Duration = last observation date – first observation date + 1.

For conversion of days to months or years the following rules will be applied:

- 1 month = 30.4375 days
- 1 year = 365.25 days

Trial Day and Treatment Day will be calculated for each trial part (1A and 1B) as follows:

- Trial day:
 - If assessment date < treatment start date then trial day = assessment date – treatment start date
 - If assessment date >= treatment start date then trial day = assessment date – treatment start date + 1
- Treatment Day = treatment date – date of first dose of BNT411 +1

That is, trial day 1 indicates the date of treatment initiation.

For BNT411, it is Cycle 1 Day 1 of Part 1A and Cycle 1 Day 2 of Part 1B. For atezolizumab, carboplatin and etoposide it is Cycle 1 Day 1 of Part 1B.

All trial data will be presented as collected in the eCRF/visit assigned in external data. No windowing of data for the purposes of assigning to a visit will occur.

Unscheduled assessments will be listed only and not included in summaries/analysis.

Handling missing data:

For the purposes of assigning treatment-emergent flag for adverse events (AEs), partial or missing AE dates will be handled as follows (trial treatment date is the earliest date of BNT411 in Part 1A and earliest date of atezolizumab, BNT411, carboplatin and etoposide in Part 1B).

- If the day of the month is missing, the onset day will be set to the first day of the month unless it is the same month and year as trial treatment. In this case, in order to conservatively report the event as treatment-emergent, the onset date will be assumed to be the first date of trial treatment.

- If the onset day and month are both missing, the day and month will be assumed to be January 1, unless the event occurred in the same year as the trial treatment. In this case, the event onset will be coded to the day and month of treatment in order to conservatively report the event as treatment-emergent.

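### Grade 3-4 lymphopenia judged not clinically significant is counted by CTCAE grade in no planned table: it is not an AE, and SAP 8.5.3 tabulates laboratory values without grade

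*SAP*

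**What the plan says.** Protocol 2.3.1.1 describes lymphopenia from redistribution as an expected effect of TLR7 agonists and adds: "Frequent laboratory monitoring is planned to observe this expected effect". In Part 1A (Protocol Table 1-1) haematology is drawn on Days 1, 2, 3, 8 and 15 of Cycles 1-2.

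Three protocol rules depend on the investigator's view of clinical significance:

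- Protocol 10.3.3, on abnormal laboratory results, makes an abnormality clinically significant if it is a sign of disease, produces symptoms, or leads to a treatment change or medical intervention. Abnormalities "for which none of the above-mentioned criteria are applicable are not clinically significant and should therefore not be documented as an AE".
- Protocol 10.3.1 gives, as its example of a finding that is not an AE, an abnormal value without clinical manifestation, "such as transient lymphopenia after infusion of BNT411 due to redistribution), should not be documented as an AE". It sets no grade limit.
- The immune-related DLT lists in Protocol 6.6.1 and 6.6.2 exempt, up to Grade 4, "lymphopenia which is not considered clinically significant by the investigator".

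In the SAP, grade appears in 8.5.2: "The number and percentage of patients with TEAEs will be summarized by worst NCI-CTC grade by PT nested within SOC". SAP 8.5.3 gives laboratory values as descriptive statistics and change from baseline per scheduled visit, as listings with abnormal values flagged, and in one categorical form: "Abnormal and clinically significant, abnormal and not clinically significant, and normal laboratory values will be summarized for each parameter by visit and cohort". Two rules in SAP 8.1 decide which values reach a summary: "Unscheduled assessments will be listed only and not included in summaries/analysis"; and "if there are multiple post-baseline assessments available within a visit/day, the earliest value and corresponding date/time will be considered".

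**The concern.** A single subjective judgement decides whether a low lymphocyte count is an AE, whether it can be a DLT under the immune-related lists, and which laboratory category it falls in. No count based on the measured value stands beside that judgement. A patient with a Grade 4 count judged not clinically significant falls in the same category as a patient marginally below the normal range.

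The safety profile is a primary objective, and this is a named, expected drug effect. As planned, the first-in-human report would not tabulate how often it reached Grade 3 or 4 at each dose in these cases; a reader would have to count from the listings. The two rules in SAP 8.1 add to this: if a patient's nadir falls on an unscheduled sample, or on a later sample within a visit, it is in no summary at all.

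The SAP takes a different line elsewhere. Section 8.5.5 counts patients in numeric QTcF categories in addition to the normal/abnormal interpretation. Lymphocytes get only the interpretation.

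**Working it through.** The plan states no figure to reproduce. The check has two parts.

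**1. Does any planned output give the count?**

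| Planned output | Contains lymphopenia judged not clinically significant? | Gives patients by grade? |
|---|---|---|
| TEAE tables by worst grade and Grade 3 or higher (SAP 8.5.2) | No, it is not an AE | Yes, for AEs |
| DLT table (SAP 8.5.2) | No, where the immune-related exemption applies | Not by grade |
| Descriptive statistics by visit (SAP 8.5.3) | Yes, scheduled values | No |
| Three-class table by visit (SAP 8.5.3) | Yes, scheduled values | No |
| Listings (SAP 8.5.3) | Yes | No; count by hand |
| Shift table (SAP 8.5.7) | No, ECOG status only | No |

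**2. Could the count be inferred from the planned statistics?**

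Inputs: cohort size up to 14 by backfilling (Protocol 4.1.1.1) and 3 to 6 otherwise (Protocol 9.2); statistics n, mean, SD, median, minimum and maximum (SAP 8.1). The documents give no grade limits, so these are assumptions: Grade 3 below 0.5 x10^9/L, shown for 0.4 to 0.6; lower limit of normal 0.8 to 1.2.

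Two constructed cohorts of 14 at one visit (unit 0.01 x10^9/L):

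- A: 15, 15, 20, 50, 55, 60, 60, 60, 125, 125, 130, 140, 200, 200
- B: 15, 30, 35, 35, 35, 45, 45, 75, 130, 140, 145, 155, 170, 200

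Both have sum 1255 and sum of squares 164925.

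- Mean = 1255/14 = 89.6, that is 0.896.
- SD = sqrt[(164925 - 1255²/14)/13] = sqrt(52423.2/13) = 63.5, that is 0.635.
- Median: A (60 + 60)/2 = 60; B (45 + 75)/2 = 60; that is 0.60 in both.
- Minimum 0.15 and maximum 2.00 in both.
- Abnormal: 8 of 14 in both, for any lower limit of normal from 0.8 to 1.2.
- Change from baseline is also the same if all baselines are equal.

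| Assumed Grade 3 limit (x10^9/L) | Patients below, A | Patients below, B |
|---|---|---|
| 0.4 | 3 | 5 |
| 0.5 | 3 | 7 |
| 0.6 | 5 | 7 |

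Cohorts of six are more constrained. In a grid search (step 0.05, minimum 0.15, maximum 1.80), sets with the same sum, sum of squares, median and number below 1.0 differed by at most one in the count below 0.5. For example, on a finer grid, 0.30, 0.31, 0.31, 0.50, 0.64, 0.90 and 0.30, 0.30, 0.33, 0.48, 0.65, 0.90 share mean 0.4933, SD 0.2415, median 0.405, minimum and maximum. They have 3 and 4 values below 0.5.

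Across visits: if 2 of 6 patients are affected on Day 2 and 2 of 6 on Day 3, the number ever affected lies between max(2, 2) = 2 and min(6, 2 + 2) = 4. A table by visit cannot narrow this.

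**The case against.** The case for leaving the SAP as it is has substance.

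- **Narrower group.** Protocol 10.3.3 also gives a wider, non-exhaustive list of medical consequences, including prompt further investigation and impact on upcoming dosing. Lymphopenia that is worked up, treated or delays a dose becomes an AE and is graded. The documents do not show how many cases remain outside. This stands, but it does not supply the count for those that do.
- **Pharmacology, not toxicity.** The protocol attributes the effect to redistribution, with return in 24 to 48 hours. Tabulating it as Grade 3-4 may mislead without explanation. A sentence in the report deals with that.
- **Nadir largely sampled.** Part 1A schedules haematology on Days 2 and 3, and Part 1B on Day 3, so most nadirs should fall at scheduled visits, where the minimum is reported. This shows how low values fell, not in how many patients.
- **Constructed example.** Backfilling to 14 is optional, and with six patients a single-visit count is almost fixed. This is fair; the across-visit ambiguity remains at six.
- **Recoverable data.** All values are listed, and cohorts are small. That is true, but hand-counting from listings is not a planned analysis.
- **Breadth of remedy.** The argument is strongest for lymphocytes. Transaminases and bilirubin have numeric DLT limits and no comparable exemption, so including them is for consistency rather than to close this gap.

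**Conclusion.** The concern holds. For lymphopenia judged not clinically significant, no planned table gives the number of patients by CTCAE grade per cohort, and the planned statistics do not determine it. At one visit the ambiguity reaches 3 versus 7 of 14 in a fully backfilled cohort, at an assumed limit of 0.5 x10^9/L (3 versus 5 at 0.4; 5 versus 7 at 0.6). In cohorts of six it was at most one patient. Across two visits with 2 of 6 affected at each, it is 2 to 4 patients.

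The 14-patient sets are illustrations, not predictions. They rest on the assumed limits and, for change from baseline, on equal baselines. Clinically significant cases are graded as TEAEs, raw values are listed, and SRC dose decisions do not rest on this table. The gap is in how the safety profile is reported. It should be closed, but it does not threaten the conduct of the trial.

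**What to change.** Amend SAP 8.5.3 to derive the NCI CTCAE v5.0 grade from the numeric value for gradeable parameters, regardless of the clinical-significance flag: at least haematology including lymphocytes, plus transaminases and bilirubin. SAP 8.5.3 drops qualifiers in summary statistics; for grading, a result reported as less than x should count as below x. By cohort, tabulate:

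1. patients by grade at each scheduled visit, including the Day 2 and Day 3 samples of Cycles 1-2 where taken;
2. worst post-baseline grade, and shift from baseline to worst grade, including unscheduled and repeat values.

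State item 2 as an exception to the unscheduled-value and earliest-value rules of SAP 8.1. Keep the clinical-significance table as secondary.

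The cost is a few extra tables from data already collected, with no new sampling. The laboratory tables will show more Grade 3-4 findings than the AE tables, and the report needs a sentence saying why.
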